7.2 PATIENT REPLACEMENT

Patients receiving less than 6 doses (60% planned dosing) will be replaced.

7.3 DETERMINATION OF SAMPLE SIZE

The primary endpoint is overall responsive rate at Day 84. Assuming Neihulizumab has a responsive rate of 44.6% (6.8 % higher than conventional treatment and 20% higher than control rate), 40 patients in Neihulizumab treatment is estimated to have > 80% power to detect the difference with a 1 sided significance level of $\alpha = 0.1$

8. REGULATORY CONSIDERATIONS

The trial will be carried out in compliance with the protocol, the principles laid down in the Declaration of Helsinki, in accordance with the ICH Harmonized Tripartite Guideline for Good Clinical Practice (GCP). Standard medical care (prophylactic, diagnostic and therapeutic procedures) remains in the responsibility of the treating physician of the patient.

The investigator should inform the sponsor immediately of any urgent safety measures taken to protect the study patients against any immediate hazard, and also of any serious breaches of the protocol/ICH GCP.

The rights of the investigator and of the sponsor with regard to publication of the results of this trial are described in the clinical trial contract with the trial institute and/or investigator. As a general rule, no trial results should be published prior to finalization of the Clinical Trial Report.

Insurance Cover: The terms and conditions of the insurance cover are made available to the investigator and the patients via documentation in the ISF or upon request.

8.1 INSTITUTIONAL REVIEW

The protocol, the proposed informed consent and all forms of participant information related to the study (e.g., advertisements used to recruit participants) will be reviewed and approved by the IRB. Any changes made to the protocol will be submitted as a modification and will be approved by the IRB prior to implementation. The site PI will disseminate the protocol amendment information to all participating investigators.

8.2 INFORMED CONSENT

This trial will be initiated only after all required legal documentation has been reviewed and approved by the respective Institutional Review Board (IRB) / Independent Ethics Committee (IEC) and competent authority (CA) according to national and international regulations. The same applies for the implementation of changes introduced by amendments.

Prior to patient participation in the trial, written informed consent must be obtained from each patient (or the patient's legally accepted representative) according to ICH GCP and to the regulatory and legal requirements of the participating country.

Informed consent will be obtained from the HCT patient patients by the investigator or his representative. The rationale, risks and benefits, and study procedures will be reviewed with the patient. Alternative therapies will be discussed. Patients will be given ample time to ask questions and do not need to sign the consent form until they are ready to proceed. Patients will be notified that they may withdraw their consent any time during the study.

The patient must be informed that his/her personal trial-related data will be used by AbGenomics in accordance with the local data protection law. The level of disclosure must also be explained to the patient.

The patient must be informed that his/her medical records may be examined by authorized monitors (CRA) or Clinical Quality Assurance auditors appointed by AbGenomics, by appropriate *IRB/IEC* members, and by inspectors from regulatory authorities.

During the consent process, the investigator or his representative will ask the patient questions to assess their understanding of the study and consent. Each signature must be personally dated by each signatory and the informed consent and any additional patient-information form retained by the investigator as part of the trial records. The investigator will store the original, signed informed consent form and any additional patient-information form per institutional policy. A signed copy of the informed consent and any additional patient information must be given to each patient or the patient's legally accepted representative. This process will be documented in the patient's record.

For patients who are not fluent in English, the consent procedure will be performed with an interpreter present (or via telephone), or a sign language-capable interpreter for those that are hearing-impaired.

8.3 DATA MONITORING PLAN

Primary internal data monitoring will be performed continuously over the accrual and follow-up periods by the site PI and the Study Coordinator. The site PI will review data to assure the validity of data, as well as the safety of the patients. The site PI will also monitor the progress of the trial. The site PI will be responsible for maintaining the clinical protocol, reporting adverse event, assuring the consent is obtained and documented, reporting of unexpected outcomes and reporting the status of the trial in the continuing renewal report submitted annually to the IRB and SRC if applicable.

8.4 DATA MANAGEMENT PLAN

This study will use Case Report Forms (CRFs) to record all protocol-related and study specific information on each trial participant, for data analysis.

8.5 DATA QUALITY ASSURANCE

A quality assurance audit/inspection of this trial may be conducted by the sponsor or sponsor's designees or by IRBs/IECs or by regulatory authorities. The quality assurance auditor will have

access to all medical records, the investigator's trial-related files and correspondence, and the informed consent documentation of this clinical trial.

8.6 REPORTING MECHANISM

The site PI (or designee) will be responsible for the coordination of all protocol amendments. Any changes to the protocol or consent will be approved by IRB prior to implementation. This process will be included in the monitoring plan. Changes or amendments to the protocol or consent will be reported to the IRB and FDA. All IRB actions will be reported to FDA.

8.7 TRIAL RECORDS

Case Report Forms (CRFs) for individual patients will be provided by the sponsor, either on paper or via remote data capture. For drug accountability, refer to [Section 4.1.4](#). Research records will be maintained in a secure office, and electronic data will be maintained in a study-specific, secure database.

8.7.1 Source documents

Source documents provide evidence for the existence of the patient and substantiate the integrity of the data collected. Source documents are filed at the investigator's site.

For eCRFs, all data must be derived from source documents. Data entered in the eCRFs must be consistent with the source documents or the discrepancies must be explained. The investigator needs to request previous medical records or transfer records, depending on the trial; also current medical records must be available.

8.7.2 Direct access to source data and documents

The investigator/institution will permit trial-related monitoring, audits, IRB/IEC review and regulatory inspection, providing direct access to all related source data/documents. CRFs/eCRFs and all source documents, including related medical records, progress notes and copies of laboratory and medical test results must be available at all times for review by the sponsor's clinical trial monitor, auditor and inspection by health authorities (e.g. FDA). The Clinical Research Associate (CRA)/on site monitor and auditor may review all CRFs/eCRFs, and written informed consents. The accuracy of the data will be verified by reviewing the documents described in [Section 8.7.1](#).

10. APPENDICES

10.1 PROCEDURES FOR PREPARING NEIHULIZUMAB FOR INTRAVENOUS ADMINISTRATION

All steps will be done at room temperature.

Have IV infusion set ready: IV tubing must be able to be used with appropriate infusion pump to precisely control flow rate (NOTE: flow rate for all groups will be fixed at 1.67 mL/min).

Proximal end of IV infusion tubing is inserted into appropriate portion of 100 mL IV infusion bag of normal saline (0.9% NaCl). Distal end of IV infusion set is inserted into the tubing end of a 25G x 3/4 inch butterfly infusion set. An infusion set of similar size can be used as long as the infusion rate can be controlled at 1.67 mL/min.

Note that throughout the following preparation procedures the maximum holding time at each step should not exceed 10 min except the time between preparation and administration to the patient which should not exceed 90 min. Preparation will be done under aseptic conditions.

Required items for preparation (refer to the respective dosing sections below for quantities):

- Vial(s) of AbGn-168H (concentration of antibody in stock solution is 40 mg/mL)
 - Standard 10 mL syringe (BD 300912 or equivalent)
 - #20 gauge needle (Braun 4657500 or equivalent)
 - IV tubing (non-DEHP, 0.2 micron filter i.e Paclitaxel 2C7558 or equivalent)
 - IV infusion bag of 100 mL normal saline (Braun S8004-5264 non-DEHP or equivalent).
 - 25G x 3/4 inch butterfly infusion set (Exel International 26708 or equivalent/similar)
1. Use a 10 ml syringe with #20 gauge needle attached to remove appropriate amount of saline solution from the 100 mL 0.9% NaCl (normal saline) bag according in the patient's weight in kg, as shown in the following table. Discard the removed saline.
 2. Inject the required volume of AbGn-168H, as shown in the table above into the reduced 100 mL saline bag and mix gently. Syringes to be used here are the same type as those for removing saline solution from the 0.9% saline.
 3. Within 90 minutes of starting the preparation, start the infusion of the saline solution at 1.6-1.7 mL/min, for a total of approximately 100 mL over about 1 hr (60 minutes).

9 mg/kg Neihulizumab dosing table

Weight (Kg/lb)				Volume of saline to be withdrawn out of saline bag	Volume of Neihulizumab to be injected into saline bag
at least		and less than			
Kg	lb	Kg	lb	(mL)	(mL)
40	88.2	45	99.2	9	9
45	99.2	50	110.2	10.1	10.1
50	110.2	55	121.3	11.3	11.3
55	121.3	60	132.3	12.4	12.4
60	132.3	65	143.3	13.5	13.5
65	143.3	70	154.3	14.6	14.6
70	154.3	75	165.3	15.8	15.8
75	165.3	80	176.4	16.9	16.9
80	176.4	85	187.4	18	18
85	187.4	90	198.4	19.1	19.1

Weight (Kg/lb)				Volume of saline to be withdrawn out of saline bag	Volume of Neihulizumab to be injected into saline bag
at least		and less than			
Kg	lb	Kg	lb	(mL)	(mL)
90	198.4	95	209.4	20.3	20.3
95	209.4	100	220.5	21.4	21.4
100	220.5	105	231.5	22.5	22.5
105	231.5	110	242.5	23.6	23.6
110	242.5	115	253.5	24.8	24.8
115	253.5	120	264.6	25.9	25.9
120	264.6	125	275.6	27	27
125	275.6	130	286.6	28.1	28.1
130	286.6	135	297.6	29.3	29.3
135	297.6	140	308.6	30.4	30.4

TEAE	Treatment Emergent Adverse Event

TNF α	Tumor Necrosis Factor- α
UC	Ulcerative Colitis
ULN	Upper Limit of Normal

2 INTRODUCTION

This study is designed to evaluate the efficacy and safety of Neihulizumab in patients with moderate to severe active ulcerative colitis (UC) who are refractory or intolerant to anti- TNF α and/or anti-integrin treatments.

The purpose of the statistical analysis plan (SAP) is to layout definitions and statistical methods for the planned analyses of primary, secondary, and exploratory endpoints. Anti-drug antibody (ADA) data will not be analyzed in this SAP. Those data will be included as an appendix in the final clinical study report.

The analyses described in this SAP are based upon the following study documents:

- Study Protocol, Version: Amendment 4 (November 01, 2018)
- Study Protocol, Version: Amendment 3 (April 03, 2018)
- Electronic Case Report Form (eCRF), Version 4.0 (February 20, 2019).

3 STUDY OBJECTIVES

3.1 Primary Objective

The primary objective of the study is to evaluate efficacy of AbGn-168H administered intravenously in patients with moderate to severe active ulcerative colitis who are refractory or intolerant to anti-TNF and/or anti-integrin treatments.

3.2 Secondary Objective

The secondary objective is to investigate safety, tolerability, and immunogenicity of intravenous AbGn-168H administration.

3.3 Exploratory Objective

Exploratory objective is to explore the change of biomarkers (faecal calprotectin and c-reactive protein) after intravenous AbGn-168H administration.

4 INVESTIGATIONAL PLAN

4.1 Overall Study Design and Plan

This is a single arm, open label, multiple dose, multi-center study to be conducted in 12-18 centers in United States (US) in 30-40 patients with a diagnosis of moderate to severe active ulcerative colitis, refractory or intolerant to anti-TNF α and/or anti-integrin treatments. Due to the COVID-19 pandemic, the holding of patient enrollment, as well as slow patient enrollment prior to the pandemic, the study has been closed out and the data will be analyzed at this time. Therefore, only available data from the patients will be included in the analysis.

Per protocol amendment 4, a total of 10 doses of Neihulizumab at 9 mg/kg will be administered to patients over 12 weeks on Day 1 (Week 0), Day 8 (Week 1), Day 15 (Week 2), Day 22 (Week 3), Day 29 (Week 4), Day 36 (Week 5), Day 43 (Week 6), Day 50 (Week 7), Day 64 (Week 9), and Day 78 (Week 11).

Whereas the patients enrolled under Protocol amendments 1-3, a total of 8 doses of Neihulizumab at 9 mg/kg are administered on Day 1 (Week 0), Day 8 (Week 1), Day 15 (Week 2), Day 22 (Week 3), Day 29 (Week 4), Day 43 (Week 6), Day 57 (Week 8), and Day 71 (Week 10).

Patients will be followed up on Day 84 (Week 12, End of Treatment, primary endpoint), Day 112 (Week 16), Day 140 (Week 20) and Day 182 (Week 26, End of Study) after the first dose of Neihulizumab.

4.1.1 Mayo Diary Card

During the screening visit, patients will be provided the Mayo diary card and instruction to fill the cards. Study coordinator will collect the Mayo diary card from patients at each visit to calculate Mayo Clinic Score (MCS) according to the subscores of stool frequency and rectal bleedings from the 3 consecutive days closest to the visiting day.

Rectal bleeding will be scored using 0-3 scale: 0 = no blood seen, 1 = streaks of blood with stool less than half the time, 2 = obvious blood with stools most of the time, 3 = blood alone passed.

Stool frequency will be recorded using 0 to 3 scale: 0 = normal, 1 = 1-2 stools/day more than normal, 2 = 3-4 stools/day more than normal, 3 = 5 or more stools/day more than normal.

4.1.2 Physician's assessment

Physician's assessment will be evaluated at each visit for the improvement of the disease activity. This score will be used to calculate the complete Mayo Clinic Score (cMCS) and partial Mayo Clinic Score (pMCS).

Physician global assessment will be evaluated by the investigator (or designee) at each visit using 4-point score system: 0 = normal, 1 = mild, 2 = moderate, 3 = severe.

4.1.3 Endoscopic Subscore

Endoscopic subscore will be assessed by a central reader.

Endoscopic findings will be evaluated using 4-point score system: 0 = normal or inactive disease, 1 = mild disease, 2 = moderate disease, 3 = severe disease.

An adjudication review will be triggered if there is a discrepancy of the change in endoscopic subscore between local and central reading. The central adjudicating reviewer will be blinded to which overall Mayo endoscopy subscore was provided by the site gastroenterologist or by the central reviewer. The adjudication assessment will be considered as final score.

4.1.4 cMCS and pMCS

The cMCS is calculated by summing the scores of following 4 assessments at Screening, W12 and W26 : Rectal bleeding, Stool frequency, Physician global assessment, and Endoscopic findings. The total score of cMCS is ranges from 0 to 12.

The pMCS will be calculated as the total of Rectal bleeding, Stool frequency, Physician global assessment without endoscopic subscore. The total score of pMCS ranges from 0 to 9.

4.2 Endpoints

4.2.1 Efficacy Variables

Efficacy will be assessed by cMCS, pMCS, endoscopy, biopsy, Inflammatory Bowel Disease Questionnaire (IBDQ), and Biomarkers (faecal calprotectin and c-reactive protein).

The **primary efficacy endpoint** is proportion of clinical responders at Week 12.

The clinical responder is defined as a \geq 3-point reduction in MCS, a 30% or greater decrease from the baseline score, and with a 1-point or greater decrease of the rectal bleeding subscale or an absolute rectal bleeding score of 0 or 1 at Week 12.

Secondary efficacy endpoints are:

1. The proportion of patients with clinical response at Weeks 6, 7, 9 and 11 defined as a ≥ 2 -point decrease in pMCS, and with a 1-point or greater decrease of the rectal bleeding subscale or an absolute rectal bleeding score of 0 or 1.
2. The proportion of patients with clinical remission, defined as MCS of 2 or lower (or pMCS of 1 or lower) and no subscore higher than 1 at Weeks 6, 7, 9, 11 and 12.
3. The proportion of responders who remain in clinical response and remission at Weeks 16, 20, and 26.
4. Flexible sigmoidoscopy subscore changes from baseline at Weeks 12 and 26.
5. The proportion of patients with sigmoidoscopic improvement, defined as any decrease in MCS endoscopic subscore, at Week 12 and 26.
6. The proportion of patients with mucosa healing defined as an absolute subscore for endoscopy of 0 or 1 at Weeks 12 and 26.
7. Change of histological activity grade from baseline at Weeks 12 and 26 using the Geboes system.
8. The proportion of patients with histological healing defined as histological grade = 0 at Weeks 12 and 26.
9. Change of Inflammatory Bowel Disease Questionnaire (IBDQ) from baseline at Weeks 12 and 26.
10. The proportion of patients with IBDQ response, defined as an increase from baseline of at least 16 points at Weeks 12 and 26.

Above time points are for the patient enrolled under Protocol Amendment 4. The time points for the patient enrolled under Amendments 1-3 are given in the table in the SAP section 4.5.2 as well as in Appendix 1 'Schedule of Assessments (Protocol Amendment 1-3)' and Appendix 2 'Schedule of Assessments (Protocol Amendment 4)'.

4.2.2 Safety Variables

Safety will be assessed by adverse event (AE) monitoring, laboratory tests, vital signs, physical examinations, discontinuation of treatment due to AE and immunogenicity.

4.2.2.1 Adverse Events

Adverse event (AE) will be coded using the Medical Dictionary for Regulatory Activities (MedDRA) version 20.1. AE will be graded according to CTCAE Version 4.03.

An AE will be considered treatment-emergent (TEAE) if it occurs on or after the first dose of the study medication or it started before the date of the first dose of study medication and worsened after the date of first dose.

Drug-related adverse events are those assessed by investigator as being definitely related, probably related, or possibly related.

Where dates are missing or partially missing, AEs will be assumed to be TEAE, unless there is clear evidence to suggest that AE started prior to the first dose of study treatment. Imputation of partial missing dates will be discussed in section 4.2.1.

Missing relationship to study drug is considered as treatment related in the analyses.

4.2.2.2 Laboratory Safety Tests

Following laboratory safety tests will be performed:

- **Hematology:** Haematocrit (Hct), Haemoglobin (Hb), Red Blood Cell / Erythrocytes Count, White Blood Cells / Leucocytes Count Platelet / Thrombocytes Count.
- **Diff Automatic:** Neutrophils (Relative and absolute Count), Eosinophils (Relative and absolute Count), Basophils (Relative and absolute Count), Monocytes (Relative and absolute Count), Lymphocytes (Relative and absolute Count).
- **Diff Manual (if Diff Automatic is abnormal):** Neutrophils, Bands (Stabs), Neutrophils, Polymorphonuclear (PMN), Eosinophils, Basophils, Monocytes, Lymphocytes.
- **Enzymes:** AST/GOT, SGOT, ALT/GPT, SGPT, Alkaline Phosphatase (AP/ALP), Lactic Dehydrogenase (LDH).
- **Substrates:** Glucose, Creatinine, Blood urea nitrogen, Bilirubin Total, Bilirubin Direct, Protein Total.
- **Hormones:** Serum β -Human Chorionic Gonadotrophin (pregnancy test) (only female patients of childbearing potential).
- **Electrolytes:** Calcium, Sodium, Potassium

4.2.2.3 Vital Signs, Physical Examination and Electrocardiograph

Vital signs: Per protocol amendment 4, the vital signs will be evaluated at screening, baseline (week 0), weeks 1, 2, 3, 4, 5, 6, 7, 9, 11, 12 [end of treatment (EOT)], 16, 20 and 26 [end of study (EOS)]. Whereas the patients enrolled under Protocol amendments 1-3, vital signs will be evaluated at screening, baseline, weeks 1, 2, 3, 4, 6, 8, 10, 12, 16, 20, 26 (EOS). Vital signs will include systolic and diastolic pressure, temperature, heart rate, and respiratory rate.

Physical examination: The patients enrolled under protocol amendment 4, full physical examination will be performed at screening, baseline, week 12 (EOT) and week 26 (EOS). The partial physical examination will be performed at weeks 1, 2, 3, 4, 5, 6, 7, 9, 11, 16 and 20. All clinically significant abnormal findings at the screening visit will be recorded in the Medical History form. Any clinically significant changes from the screening visit will be recorded. The patients enrolled under protocol amendment 1-3, full physical examination will be done at same time points as subject enrolled under amendment 4. However, the partial physical examination will be performed only at weeks 1, 2, 3, 4, 6, 8, 10, 16, and 12.

Electrocardiograph (ECG): 12-Lead resting ECG will be performed at Screening visit.

4.2.3 Exploratory Efficacy Biomarkers

Exploratory efficacy endpoints are faecal calprotectin and c-reactive protein changes at Weeks 4, 9, 12, 16, 20, and 26.

4.2.4 Pharmacokinetic and Anti-drug Assessments

Blood samples for Pharmacokinetic (PK) determinations will be drawn approximately 15 minutes before dosing and 2 hours post dosing at Visits 2, 9 and 11, 15 minutes before dosing at Visits 3, 4, 5, 6, 7, 8 and 10, and at Visits 12, 13 and 14. The plasma concentration (Cmax) and associated parameters will be calculated at Day 1, Day 50, and Day 78. The PK profile will be monitored as specified in Table 1 of the Appendix 1 Schedule of assessments of the SAP.

Anti-drug antibodies (ADA) will be determined in all patients before dosing at Visits 2, 6, 10 and at Visits 12-15.

5 STATISTICAL METHODS

5.1 Data Quality Assurance

All tables, figures and data listings to be included in the report will be independently checked for consistency, integrity and in accordance with standard PAREXEL procedures.

5.2 General Presentation Considerations

Due to the small number of patients expected to be enrolled at each center, all summaries and analyses will be performed using pooled patients across centers.

Unless otherwise specified, continuous data will be summarized with the number of non-missing observations, in terms of the mean, standard deviation (SD), median, minimum, maximum and number of observations, unless otherwise stated. Continuous data that are expected to be skewed will be presented in terms of the maximum, upper quartile, median, lower quartile, minimum and number of observations. The minimum and maximum will be reported to the same number of decimal places as the raw data recorded in the database. The mean, median, lower quartile and upper quartile will be reported to one more decimal place than the raw data recorded in the database. The SD will be reported to two more decimal places than the raw data recorded in the database. In general, the maximum number of decimal places reported shall be four for any summary statistic.

Categorical data will be summarized in terms of the number of patients providing data at the relevant time point (n), frequency counts and percentages.

Percentages will be presented to one decimal place. Percentages will not be presented for zero counts.

Confidence intervals will be presented to one more decimal place than the raw data.

The patients enrolled under Protocol amendments 1-3 were administered 8 doses of study medication over 11 weeks whereas the patients enrolled under amendment 4 will be administered

10 doses over 12 weeks. Therefore, the statistical analyses and summary tables will be performed by following groups: Group 1: the patients enrolled under amendments 1 to 3, Group 2: the patients enrolled under amendment 4.

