5.5.1 Analysis Sets

The study populations include the ITT, modified ITT (mITT), safety, and PK sets.

Intent-to-Treat Set: The ITT population is defined as all patients who are enrolled irrespective of treatment received or not.

Modified Intent-to-Treat Set: The mITT set is defined as all patients who are enrolled and have received at least one dose of Neihulizumab treatment.

The efficacy analyses will be based on the modified ITT set. Summaries of patient disposition, demographics, and disease characteristics, assessments of physical condition and functionality, and dosing of study drug will be provided in this population.

Safety Set: Safety set includes all patients in mITT. This analysis set will be used for all safety analyses and analysis of exposure.

Pharmacokinetic Set: This set will include all patients in mITT who provide at least one post-baseline evaluable drug concentration value.

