5.9.2 Primary Efficacy Endpoint

The primary efficacy endpoint is the proportion of clinical responders at week 12. The clinical response is a composite measurement of MCS and the rectal bleeding score. It is defined as:

a) ≥ 3-point reduction in MCS, a 30% or greater decrease from the baseline score,

AND

b) 1-point or greater decrease of the rectal bleeding subscale or an absolute rectal bleeding score of 0 or 1 at Week 12.

The proportion of response rate will be summarized with frequencies and percentages along with 2-sided 95% exact Clopper-Pearson confidence interval at Week 12.

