5.14 Determination of Sample Size

The primary endpoint is overall responsive rate at Day 84. Assuming placebo effects of 25% (historical data) and AbGn-168H responsive rate of 45%, 40 patients have > 80% power to detect an alpha of 0.1 (two sided).

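### SAP 5.2 splits the analyses by amendment group and specifies no pooled estimate of the Week 12 response rate, although the sample size was set for the whole trial

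*SAP*

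**What the plan says.** SAP 5.2 notes that patients under Amendments 1 to 3 received 8 doses and those under Amendment 4 receive 10. It concludes: "Therefore, the statistical analyses and summary tables will be performed by following groups". The groups are "Group 1: the patients enrolled under amendments 1 to 3, Group 2: the patients enrolled under amendment 4". No total is listed. The pooling sentence earlier in 5.2 concerns centres, not amendments.

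SAP 5.9.2 sets out the primary analysis: "The proportion of response rate will be summarized with frequencies and percentages along with 2-sided 95% exact Clopper-Pearson confidence interval at Week 12". It names neither the groups nor a total. SAP 5.9.3 does not name them for the secondary endpoints either.

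Other places treat the trial as one population:

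- SAP 5.5.1: "The efficacy analyses will be based on the modified ITT set". That set is not defined by amendment: "The mITT set is defined as all patients who are enrolled and have received at least one dose of Neihulizumab treatment".
- The statistical methods entry of the protocol synopsis includes all treated (mITT) patients in all analyses. Protocol 7.1 and 7.1.3 base the analyses on the same set, with no split.
- SAP 5.14 gives one sample size for the trial: "Assuming placebo effects of 25% (historical data") and a response rate of 45%, "40 patients have > 80% power" at a two-sided alpha of 0.1.

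SAP 4.1 adds that enrolment was slow and then held, so that "the study has been closed out and the data will be analyzed at this time". The achieved number of patients is not stated.

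**The concern.** The trial has one primary objective, one primary endpoint and one sample size. A programmer who follows SAP 5.2 to the letter would produce two columns and no total, so the primary endpoint would be reported as two proportions, each on part of the patients. The SAP does not say which of them answers the objective.

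Two things are at stake. The first is precision: each group's interval is wider than the interval from all treated patients. The second is pre-specification. The trial is open-label, and the SAP carries an approval date of 20 October 2020 and already describes the close-out. If the primary estimate is not named, the 8-dose rate, the 10-dose rate or a later pooled rate could each be presented as the main result once outcomes are known.

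**Working it through.** **Inputs.** Reference rate p0 = 0.25, assumed response rate p1 = 0.45, N = 40, two-sided alpha 0.10, i.e. 0.05 in the upper tail (SAP 5.14). Interval method: exact Clopper-Pearson, 95% (SAP 5.9.2). Group sizes are not in the documents. A 20/20 split is assumed, with 30/10 as a second case.

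**1. The plan's own figure.** For a one-sample comparison with a fixed 25%, normal approximation:

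power = Φ( [ (p1 − p0)√n − 1.645·√(p0(1 − p0)) ] / √(p1(1 − p1)) )

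At n = 40: (0.20 × 6.325 − 1.645 × 0.4330) / 0.4975 = (1.2649 − 0.7123) / 0.4975 = 1.111, and Φ(1.111) = 86.7%.

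The exact binomial version takes the smallest count r with P(X ≥ r | 0.25) ≤ 0.05. That is r = 16, with tail probability 0.026, and P(X ≥ 16 | 0.45) = 78.6%. The stated figure of more than 80% is reproduced by the normal approximation. The exact version falls 1.4 points short. The figure applies to all 40 patients together.

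**2. The same calculation by group, at the SAP's alpha.**

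| n | Smallest r | Tail probability at 25% | Exact power at 45% | Normal approximation |
|---|---|---|---|---|
| 40 (pooled) | 16 | 0.026 | 78.6% | 86.7% |
| 30 | 13 | 0.022 | 64.1% | 77.9% |
| 20 | 9 | 0.041 | 58.6% | 64.3% |
| 10 | 6 | 0.020 | 26.2% | 43.6% |

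**3. Precision with the planned 95% exact interval, at an observed rate as near 45% as the count allows.**

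Lower limit = Beta quantile (0.025; x, n − x + 1). Upper limit = Beta quantile (0.975; x + 1, n − x).

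| Result | 95% interval | Width (points) |
|---|---|---|
| 18/40 | 29.3% to 61.5% | 32 |
| 14/30 | 28.3% to 65.7% | 37 |
| 9/20 | 23.1% to 68.5% | 45 |
| 4/10 | 12.2% to 73.8% | 62 |

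**4. Sensitivity to the error level.** A two-sided alpha of 0.10 corresponds to a 90% interval, not the 95% interval of SAP 5.9.2. On a 90% interval, 9/20 gives 25.9% to 65.3%, so the lower limit is above 25%. Against the stricter 95% interval, the smallest counts that exclude 25% are 17/40, 10/20 and 6/10, and the probability of reaching them at a true 45% is 68%, 41% and 26%. The loss from splitting appears at either level. Part of the shortfall on the 95% interval comes from the stricter level and is present at n = 40 too.

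**5. Effect of early closure.** If the pooled total were only 25 or 20 (assumed), exact power at the SAP's alpha would be 61.6% or 58.6% even with everyone combined. Pooling gives the best precision available from the patients enrolled. It does not guarantee the planned 40.

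**The case against.** The strongest reply is that silence is not a prohibition. SAP 5.2 deals with presentation and does not exclude a total. The mITT set covers all treated patients, SAP 5.9.2 describes one proportion with one interval, the visit-window table in SAP 5.5.2 has a combined column for Amendments 1 to 4, and the multiple-imputation trigger in SAP 5.9.1.1 is judged overall. This stands. A reader might infer from SAP 5.2 that the overall response rate will never be estimated, and the documents do not support that: they leave a pooled result possible. But none of these places specifies one.

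A reader might also infer that neither group could distinguish 45% from 25%. That is too strong. 9/20 does so on a 90% interval, and 14/30 does so on a 95% interval. What can be said is that power is low in a group of 20 or fewer.

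The split also has a stated reason: the groups had different numbers of doses on different schedules, and the current protocol describes only the 10-dose regimen. SAP 5.14 does not say whether its 40 patients may mix regimens. This is a fair argument for displaying the groups, and it makes the choice of the pooled rate as primary debatable. It does not argue against reporting the pooled rate as well: the dose per infusion and the Day 84 assessment are common to both schedules.

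Finally, a pooled proportion can be worked out from two published counts. That is true, but a figure derived afterwards is not a pre-specified estimate.

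**Conclusion.** The point holds as a gap in specification. SAP 5.2 directs analysis by amendment group, no section specifies a pooled Week 12 response rate, and none says which estimate answers the primary objective. This sits poorly with a protocol that includes all treated patients in all analyses and with a sample size set for the whole trial.

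Under an assumed 20/20 split, the 95% interval widens from about 32 to about 45 points, and exact power at the SAP's alpha falls from 79% to 59%. These figures rest on assumed group sizes and on a total of 40. The achieved total is unknown, so some of the lost precision may be due to early closure and could not be recovered by pooling. The change should be made, but it completes the plan and does not overturn it.

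**What to change.** In SAP 5.2 and 5.9.2:

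- Add an overall (Groups 1 + 2) mITT estimate of the Week 12 response rate, with its exact confidence interval.
- Add an overall column to the safety tables, and to the efficacy tables at the visits both schedules share (Weeks 6, 12, 16, 20 and 26). Weeks 7, 9 and 11 exist only under Amendment 4, so no overall figure fits there.
- Keep the two regimen groups displayed alongside.
- State which estimate (overall, 8-dose or 10-dose) answers the primary objective, and give the reason.

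The cost is one extra column and two or three sentences. The small downside is that the overall figure mixes two dosing schedules, which the by-group columns still show.
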